## Summary of Inclusion and Exclusion Criteria for Mouthrinse RCT

Inclusion Criteria	Exclusion Criteria

Individuals (all sex, all gender) at least 18 years of age and at most 65 years of age in good oral health and with stable physical health, decided at the discretion of the study coordinator.
	
Known allergies or significant adverse reactions following the use of oral hygiene products (toothpastes, mouthrinses), commercial cosmetics, iodine, and any ingredient in the mouthrinses (list will be provided).

Diagnosed COVID+ status (within the past 48 hours) who became symptomatic in the prior 10 days, or if not symptomatic, was likely infected/exposed within the prior 10 days.
	
Established history of Xerostomia (drug-induced or autoimmune dry mouth), renal disease, thyroid problems (including swelling, Hoshimoto's thyroiditis, Goiter), Hepatitis C Virus (HCV), severe periodontal disease with bleeding gums, significant oral abrasions/ulcers or growths, alcohol abuse, recreational drug abuse, and/or current treatment with lithium. Other severe acute or chronic medical or psychiatric condition or laboratory abnormality that may increase the risk associated with trial participation or investigational product administration or may interfere with the interpretation of trial results and, in the judgment of the Investigator, would make the subject inappropriate for entry into this trial.

Evidence of a personally signed and dated informed consent document indicating the subject (or legally acceptable representative) has been informed of all pertinent aspects of the trial and all of their questions have been answered.
	
Drinking or eating within an hour of the study visit. Consuming alcohol within 12 hours of the study visit. Rinsing with a commercial mouthrinse within 24 hours of the study visit.

Able to comprehend and follow the requirements of the study (including availability on scheduled visit dates) based on research site personnel's assessment.
	
Developmental/cognitive disability such that patient cannot self-consent, comprehend and follow the requirements of the study based on research site personnel's assessment.


Females of childbearing potential will have a negative urine pregnancy test (on site) or be physically incapable of pregnancy (implants or injections, Intrauterine device, Bilateral tubal ligation, Hysterectomy, Ovariectomy, Women post-menopausal)
	
Positive pregnancy test, reported pregnancy or lactation.

	A history of recent (within the last 30 days) or current recent oral herpes flare up, candida (thrush) infection, apthous ulcer flare up, current/active severe periodontal disease with bleeding gums, or other recent oral viral infection or flare up within the past 30 days.
--	---

### 4.3 Study Enrollment Procedures

Outpatient subjects will be recruited from patients seen in the UNC Respiratory Distress Clinic (RDC) and other UNC testing facilities who have tested positive for COVID+ and consented to be contacted for participation in COVID-related research studies. The subjects are being approached by phone or email have signed a prior facility consent at the Respiratory Distress Clinic confirming their willingness to share their name and contact information to be contacted for study participation in COVID related research. We will not receive information on subjects that decline this internal consent. Subjects will be contacted for recruitment by phone and (if unreachable by phone) by secure email by study personnel; patients will have the study rationale and risks explained and will be provided time to ask questions and consider participation. If patients are interested in participating, a single appointment will be scheduled for them at the Adams School of Dentistry Go Health Clinical research core. Consent documentation will be signed in person and in private in the Go Health Clinical Research Core. For Spanish speaking patients and/or parents, Spanish forms will be provided and communication will occur through a Spanish translator. All patients are adults and over normal cognitive capacity, and therefore will be able to consent for themselves. A list of COVID+ subjects that have consented to be contacted for research, will be provided by the RDC clinic, sent via secure UNC servers or secure UNC email to our research team's clinical coordinator, and this list will include names and contact details (PHI). This list is updated daily and provided to approved research sites, including ours.

At the visit, a consented patient will answer screening questions regarding inclusion and exclusion criteria. Answers will be entered into the CDART research database managed by UNC. Prior to finalizing these screening questions, women participants of childbearing potential will be asked to provide a urine sample in the restroom, to undergo a rapid pregnancy test by study personnel. Any pregnant or lactating patients will be excluded.

Our study statistician, [name], will create a block randomization schedule and perform these computations. All patients will be consented and then fill out our screening questions for inclusion and exclusion to confirm eligibility prior to being assigned to the randomization schedule.

## 5. STUDY INTERVENTIONS

### 5.1 Interventions, Administration, and Duration

Patients who meet all inclusion criteria without any exclusions will be asked to give a baseline salivary sample of 5ml over 10 minutes. The patient will then be asked to rinse with an unlabeled/blinded antiseptic mouth rinse for 60 seconds. Once s/he expectorates the mouth rinse, a time 0, 2ml salivary sample will be collected over 5 minutes. Then the patient will have 10 minutes to recuperate, while answering survey questions about their demographics and regarding the taste, color, flavor and acceptability of using the mouth rinse as part of routine dental and medical visits. Patients will be asked to smell an ammonia ampule ('smelling salt') to evaluate sense of smell, as loss of olfaction is indicative of the acute infection phase. At 15 minutes post-rinse, the patient will be asked to provide an additional 2ml saliva samples over 5 minutes, followed by another 10 minute break. This sequence repeats for the 30, 45 and 60 minute time points. At 60 minutes, the patient will give their last 2ml salivary sample, and study participation will conclude. Participants will be provided with a gift card for their participation.

### 5.2 Handling of Study Interventions

Mouthrinses will be acquired from the following sources:

mouthrinse*	Source: Online pharmacies and reputable marketplaces with over the counter mouthrinses
26.9% ethanol plus essential oils	Listerine's Original Mouthrinse- Amazon or CVS online store
1% w/v Povidone-iodide (PVI)	Betadine Mouthrinse- Amazon or CVS online store
1.5% w/v Hydrogen Peroxide rinse	Oral B Mouth Sore Mouthrinse- Amazon or CVS online store
0.12% Chlorhexidine Gluconate	Peridex- CVS Pharmacy and Adams School of Dentistry Dispensary
0.1% Cetylpyridinium Chloride	Crest Pro-Health Mouthrinse- Amazon or CVS online store
0.9% NaCl	Amazon or CVS online store

*\*All mouthrinses are commercially available in the USA, routinely used in clinical settings, and will be used in an on-label manner.*

Mouthrinses will be prepared by research study staff under sterile conditions in a 10mL sterile syringe. The syringe will be unlabeled and opaque so both the participant and study personnel will be blinded to the color of the solution.

Any adverse events or protocol deviations will be reported to the UNC IRB. Weekly meetings of the internal quality control committee will allow us to closely monitor such events.

### **5.3 Concomitant Interventions**

There are no concomitant interventions other than the mouthrinse and a short survey.

#### **5.3.1 Allowed Interventions**

There are no additional interventions, other than mouth rinsing with one of the 6 options previously described. If patients have an allergic reaction, EMS will be contacted for management, and therefore no rescue medications are indicated.

#### **5.3.2 Required Interventions**

The patient will rinse with a blinded mouthrinse for 60 seconds and then will spit it out, followed by donating saliva samples.

#### **5.3.3 Prohibited Interventions**

Patients who have drank or eaten within an hour of the study visit will be excluded. Patients who have used a mouthrinse within 48 hours of the study will be excluded.

Patients who have participated in a study of other oral products (toothpaste, mouthrinses) within the prior 30 days will be excluded.

Patients who are abusers of alcohol or recreational drugs, and have used such products within 48 hours will be excluded.

### **5.4 Adherence Assessment**

Adherence would be defined as rinsing with the mouthrinse for a full 60 seconds before expectorating, and then providing saliva samples at 15 minute time points.

## 6. STUDY PROCEDURES

### 6.1 Schedule of Evaluations

Assessment	Screening: Visit-1 (Day-14 to Day -1)	Baseline, Enrollment, Randomization, Intervention: Visit 1 (Day 0)
Informed Consent Form	X	X
Demographics	X	X
DXA	X	X
Medical History	X	X
General Physical Examination		
Current Medications	X	X
Blood Chemistries		
Hematology		
Urine Analysis-pregnancy		X
Vital Signs		X
Inclusion/Exclusion Criteria	X	X
Enrollment/Randomization	X	X

Treatment Administration Form		X
Concomitant Medications	X	X
Adverse Events	X	X

## 6.2 Description of Evaluations

Subjects are required to be onsite for a 70-90 minute, single visit appointment. Subjects will be asked to rinse with an unlabeled/blinded antiviral mouth rinse for 60 seconds and provide 5 mL of saliva prior to the rinse and 2 mL of saliva immediately post-rinse, 15 minutes post-rinse, 30 minutes post-rinse, 45 minutes post-rinse, and 60 minutes post-rinse. Subjects will also be asked to complete a short survey about the rinsing experience.

### 6.2.1 Screening Evaluation

#### Consenting Procedure

Patients will be contacted first by phone and, if not available, then by email. The consent process will be conducted by [name]. The study's purpose and requirements will be explained and the patient will have the opportunity to ask questions and will have time to consider participation. Interested patients will make an appointment to visit the Go Health Clinical Research Unit at Adams School of Dentistry for this study. Study participation includes only one visit. The consent forms will be reviewed and signed by interested patients in person in the Go Health Clinical Research Unit at Adams School of Dentistry prior to study participation. For Spanish speaking patients and/or parents, Spanish forms will be provided and communication will occur through a Spanish translator. All patients are adults and over normal cognitive capacity, and therefore will be able to consent for themselves.

#### Screening

- At the visit, a consented patient will answer screening questions regarding inclusion and exclusion criteria. Answers will be entered into the CDART research database managed by UNC.
- Prior to finalizing these screening questions, women participants of childbearing potential will be asked to provide a urine sample in the restroom, to undergo a rapid pregnancy test by study personnel. Any pregnant or lactating patients will be excluded.

## **6.2.2 Enrollment, Baseline, and/or Randomization**

### **Enrollment**

Outpatient subjects will be recruited from patients seen in the UNC Respiratory Distress Clinic (RDC) who have tested positive for COVID+ and consented to be contacted for participation in COVID-related research studies. The subjects being approached by phone or email have signed a prior facility consent at the Respiratory Distress Clinic confirming their willingness to share their name and contact information to be contacted for study participation in COVID related research. We will not receive information on subjects that decline this internal consent. Subjects will be contacted for recruitment by phone and (if unreachable by phone) by secure email by study personnel; patients will have the study rationale and risks explained and will be provided time to ask questions and consider participation. If patients are interested in participating, a single appointment will be scheduled for them at the Adams School of Dentistry Go Health Clinical research core. Consent documentation will be signed in person and in private in the Go Health Clinical Research Core. A list of COVID+ subjects that have consented to be contacted for research, will be provided by the RDC clinic, sent via secure UNC servers or secure UNC email to our research team's clinical coordinator, and this list will include names and contact details (PHI). This list is updated daily and provided to approved research sites, including ours.

### **Baseline Assessments**

There are no baseline assessments required as this study only requires a 70-90 minute single visit appointment.

### **Randomization**

Our statistician [name] will create a block randomization schedule and perform these computations. All patients will be consented and then fill out our screening questions for inclusion and exclusion to confirm eligibility prior to being assigned to the randomization schedule.

The researcher in charge of collecting the salivary samples will be blinded to the mouthwash solution, as they will be given a pre-aliquoted mouthrinse in an unlabeled storage tube to provide to the patient for the rinse.

### **6.2.3 Blinding**

At their onsite visit, subjects will be provided with an unlabeled/blinded mouthrinse. The researcher in charge of collecting the salivary samples will be blinded to the mouthwash solution as well, as they will be given a pre-aliquoted mouthrinse in an unlabeled storage syringe to provide to the patient for the rinse. Our statistical consultant, [name],

will set up a block randomization schedule that the team will abide by for assignment of enrolled subjects.

#### **6.2.4 Follow-up Visits**

This study requires only one 70-90 minute, single visit appointment. No diagnostic tests will be run as part of this clinical trial. All participants will already have known COVID+ status, and therefore no follow-up reporting is needed.

#### **6.2.5 Completion/Final Evaluation**

This study requires only one 70-90 minute, single visit appointment. Subjects will be asked to rinse with an unlabeled/blinded antiviral mouth rinse for 60 seconds and provide 5 mL of saliva prior to the rinse and 2 mL of saliva immediately post-rinse, 15 minutes post-rinse, 30 minutes post-rinse, 45 minutes post-rinse, and 60 minutes post-rinse. Subjects will also be asked to complete a short survey about the rinsing experience.

Subjects may withdraw from the trial at any time at their own request, or they may be withdrawn at any time at the discretion of the Investigator or Sponsor for safety, behavioral or administrative reasons.

The Investigator may discontinue a subject if, in the opinion of the Investigator, the subject is no longer a suitable candidate for the study. Possible reasons for the discontinuation of a subject are including but not limited to: adverse event, protocol deviation, missed appointment, subject no longer meets the eligibility criteria.

Patients may be removed from the study due to an allergic reaction to a mouth rinse or due to failure or inability to comply with study procedures.

If a patient suffers from xerostomia/dry mouth, such that s/he cannot produce the baseline salivary sample volume or the immediate, 15 minute and 30 minute post-rinse saliva volumes, s/he will be removed from the study with a parking voucher, but without a gift card and will be replaced. If a patient suffers from dry mouth, such that s/he cannot produce salivary sample volumes needed for later time points (45 minutes or 60 minutes post-rinse) but s/he produced sufficient baseline, immediate, 15 minute and 30 minute post-rinse samples, s/he will still be compensated with a gift card and parking vouchers, and will remain in the study. Missing or deficient salivary samples will be noted in CDART.

## 7. SAFETY ASSESSMENTS

The following table lists possible adverse effects associated with each mouthrinse proposed in this study:

mouthrinse*	Adverse effects
26.9% ethanol plus essential oils	
 
• If more than used for rinsing is accidentally swallowed, get medical help or contact a Poison Control Center right away
 

1% w/v povidone-iodide (PVI)	
 
• Local irritation, skin burns and sensitivity reactions have been reported rarely.
 
• Anaphylactic reactions, anaphylactoid reactions and anaphylactic shock have been reported uncommonly with products containing povidone-iodine or povidone.
 
• Excess iodine can produce goitre and hypothyroidism or hyperthyroidism. Such effects have occasionally been seen with extensive or prolonged use of povidone iodine.
 
• Other effects that have been reported are metabolic acidosis and acute renal failure.
 
• Possible unwanted effects: Like all medicines, Betadine Gargle and Mouthwash can cause unwanted effects, although these are uncommon. Allergic-type reactions, including a rash or difficulty in breathing, have been reported uncommonly with products containing povidone iodine (the active ingredient in Betadine Gargle and Mouthwash). Although rare, Betadine Gargle and Mouthwash could also cause itching and burns on your skin. Applying very large amounts of medicines containing povidone iodine, or using such products over a long period of time, can occasionally cause thyroid disorders (symptoms of which include weight loss, increased appetite and sweating or lacking energy and weight gain). Other effects that have been reported are increased amounts of acid in your blood (the main symptoms are shortness of breath, confusion and lethargy) and kidney failure (symptoms include difficulty in urinating, thirst and a dry mouth and pain in one side of your back). Should you suffer from any of these unwanted effects, or if you notice any unwanted effects not listed in this leaflet, stop using Betadine Gargle and Mouthwash straight away and tell your doctor or pharmacist.
 

1.5% w/v hydrogen peroxide rinse	
 
• If irritation persists for 7 days, is severe, is due to orthodontic appliances and/or dentures, or swelling or fever develops, the patient's condition needs to be re-evaluated by a doctor or dentist.
 
• Overdose can injure the gums and continued use of hydrogen peroxide may cause reversible hypertrophy of the papillae of the
 

	
tongue known as ‘black hairy tongue’ therefore using this product at high doses or for long periods of time is not recommended.
 
 
• Some cases of mucosal irritation and swelling of the oral tissues have been reported specially with high doses or in continued use.
 

0.12% Chlorhexidine Gluconate	
 
• The most common side effects associated with chlorhexidine gluconate oral rinses are: (1) an increase in staining of teeth and other oral surfaces, (2) an increase in calculus formation, and (3) an alteration in taste perception; see WARNINGS and PRECAUTIONS. Oral irritation and local allergy-type symptoms have been spontaneously reported as side effects associated with use of chlorhexidine gluconate rinse. The following oral mucosal side effects were reported during placebo-controlled adult clinical trials: aphthous ulcer, grossly obvious gingivitis, trauma, ulceration, erythema, desquamation, coated tongue, keratinization, geographic tongue, mucocele, and short frenum. Each occurred at a frequency of less than 1.0%. Among postmarketing reports, the most frequently reported oral mucosal symptoms associated with chlorhexidine gluconate oral rinse are stomatitis, gingivitis, glossitis, ulcer, dry mouth, hypesthesia, glossal edema, and paresthesia. Minor irritation and superficial desquamation of the oral mucosa have been noted in patients using chlorhexidine gluconate oral rinses. There have been cases of parotid gland swelling and inflammation of the salivary glands (sialadenitis) reported in patients using chlorhexidine gluconate oral rinse.
 

0.1% Cetylpyridinium Chloride	
 
• If more than used for rinsing is accidentally swallowed, get medical help or contact a Poison Control Center right away
 

0.9% NaCl	No contraindications

*\*All mouthrinses are commercially available in the USA, routinely used in clinical settings, and will be used in an on-label manner.*

The use of on-label, widely used mouthrinses (like Listerine) and collection of saliva carry minimal risk for participants, apart from the very rare, undiagnosed allergy, and the unlikely event that the sample is swallowed. If the case of allergy, UNC Hospital emergency services will be contacted. In the case of swallowing, a Poison Control Center will be contacted.

## **7.1 Specification of Safety Parameters**

Mouthrinse and saliva collection carries low risk and minimal to no safety concerns to the participants. Results of analysis from known COVID+ patients will not require any medical follow-up or safety concerns. As a result, the investigator will monitor subject data, without a safety monitoring board. The investigator and team will meet weekly to review safety concerns, unanticipated problems or adverse events.

## **7.2 Methods and Timing for Assessing, Recording, and Analyzing Safety Parameters**

The investigators and study coordinators will meet weekly to review unanticipated problems with recruitment or adverse events. There is only one site for this study. The use of on-label, widely used mouthrinses (like Listerine) and collection of saliva carry minimal risk for participants, apart from the very rare, undiagnosed allergy, which would be managed through proper referral to the neighboring UNC hospital.

## **7.3 Adverse Events and Serious Adverse Events**

An **adverse event (AE)** is generally defined as any unfavorable and unintended diagnosis, symptom, sign (including an abnormal laboratory finding), syndrome or disease which either occurs during the study, having been absent at baseline, or if present at baseline, appears to worsen. Adverse events are to be recorded regardless of their relationship to the study intervention.

A **serious adverse event (SAE)** is generally defined as any untoward medical occurrence that results in death, is life threatening, requires inpatient hospitalization or prolongation of existing hospitalization, results in persistent or significant disability/incapacity, or is a congenital anomaly.

The use of on-label, widely used mouthrinses (like Listerine) and collection of saliva carry minimal risk for participants, apart from the very rare, undiagnosed allergy, or the unlikely event that a participant slips or falls during the study, which would be managed through proper referral to the neighboring UNC hospital.

The investigator and team will meet weekly to review safety concerns, unanticipated problems or adverse events. All adverse events will be reported to the IRB and the committee overseeing the study within 30 days.

## **7.4 Reporting Procedures**

The PI will be responsible to monitor the overall study, including both research data and clinical procedures. The PI will be responsible for reporting all adverse events to the necessary parties. The investigator and team will meet weekly to review safety concerns, unanticipated problems or adverse events. All adverse events will be reported to the IRB and the committee overseeing the study within 30 days.

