Known and potential risks include breach of confidentiality, slight discomfort, and a low chance of a previously undiagnosed allergy. To minimize risk of breach of confidentiality, all patients will be assigned a unique study ID. There will be no other subject identifiers on samples or data. The linkage file that relates patient's names to study ID numbers will be stored on a UNC secure server. All desktops computers and servers are kept in locked facilities and in accordance with UNC IT/security safeguards and policies. All providers and study researchers have been trained in and abide by HIPAA procedures, and confidential patient information will be stored on secured, encrypted UNC servers. Patients will already have been provided with their COVID status through their healthcare providers, and this confidential medical information will not be released by any study personnel. Some patients may perceive the mouth rinse as causing some discomfort if they dislike the flavor or the bubbling sensation. A small fraction of patients (rare <1%) may be allergic to the mouth rinse. We will ask detailed questions in our screening protocol if patients are allergic to any component of the mouthrinses, but if a patient answers no to all screening questions regarding allergy and then they are allergic, it may lead to an adverse allergic reaction.

The following table lists adverse effects associated with each mouthrinse proposed in this study:

mouthrinse*	Adverse effects
26.9% ethanol plus essential oils	
 
• If more than used for rinsing is accidentally swallowed, get medical help or contact a Poison Control Center right away
 

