## **7.6 Safety Monitoring**

The investigator will monitor subject data, without a safety monitoring board. The investigator and team will meet weekly to review safety concerns, unanticipated problems or adverse events.

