## **9.2 Sample Size and Randomization**

Based on similar viral infectivity studies evaluating antiviral mouth rinse efficacy, we were able to run power calculations to estimate effect size and determine sample size as a function of length of mouthrinse time course. The sample size is justified by a paired t-test on outcomes between time points. With three simultaneous comparisons (T1-T0, T2-T1, and T2-T0 = 30 minute time course), the sample size n=6 can detect the effect size in Cohen's d =0.7, which is between medium and large, under 80% power and 0.016 type-I error rate by Bonferroni correction. With six simultaneous comparisons (T1-T0, T2-T1, T2-T0, T3-T0, T3-T2, T3-T1) = 45 minute time course, the sample size n=53 can detect the effect size in Cohen's d =0.7, which is between medium and large, under 80% power and 0.016 type-I error rate by Bonferroni correction. With ten simultaneous comparisons (T1-T0, T2-T1, T2-T0, T3-T0, T3-T2, T3-T1, T4-T3, T4-T2, T4-T1, T4-T0) = 60 minute time course, the sample size n=78 can detect the effect size in Cohen's d =0.7, which is between medium and large, under 80% power and 0.016 type-I error rate by Bonferroni correction.

[name], who is the statistical consultant on this project, will create a block randomization schedule and perform these computations. All patients will be consented and then fill out our screening questions for inclusion and exclusion to confirm eligibility prior to being assigned to the randomization schedule.

The researcher responsible for collecting the salivary samples will be blinded to the mouthwash solution, as they will be given a pre-aliquoted mouthrinse in an unlabeled storage syringe to provide to the patient for the rinse. The syringe will be opaque to mask any coloring of the solution.

The PI, Co-I, study coordinators and study personnel who work for GoHealth are authorized to break the blinding if a patient suffers an allergic or adverse reaction to one of the mouthrinses. Though highly unlikely as all mouthrinses are sold commercially at Walgreens and CVS, adverse or allergic reactions are possible. Using the numerical code associated with the participant and mouthrinse syringe, the study personnel can reference the block randomization schedule to determine the mouthrinse type, to inform the emergency medical workers, poison control or the emergency room what type of mouthrinse product led to the reaction.

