### **9.4 Interim Analyses and Stopping Rules**

An interim analysis will be conducted after 120 patients are enrolled and samples collected; block randomization will be planned to randomize in batches of 120 participants, with 20 randomized to each mouthrinse. Therefore, we can do an interim analysis with an  $n=120$ . This sample size is sufficient to determine antiviral efficacy at 30 minutes post-mouthrinse. If mouthrinses are ineffective at reducing viral infectivity at timepoints 15 and 30 minutes, then that mouth rinse arm will be discontinued for further enrollment and will be removed from the block randomization calendar, with initiation of a subsequent trial with fewer arms. This will allow us to enroll sufficient numbers of patients to statistically evaluate longer time point efficacy for the mouthrinses with antiviral efficacy (the longer time points require larger samples sizes for sufficient statistical power).

If no mouthrinse has antiviral effects at this interim analysis point, the study will be stopped due to lack of efficacy. Because all oral rinse products are commercially available, low risk products that have previously undergone extensive safety testing and approval procedures, we do not anticipate a situation where safety concerns to participants necessitates halting the study. Adverse events will be reported and reviewed by our internal quality control committee. Medical problems that occur in our facility will be reported as needed to the IRB board and emergency medical personnel will be contacted to care for the patient and potentially bring them to the adjacent UNC medical hospital. If a significant number of adverse events or reactions are witnessed (defined as more than 1 per every 20 patients), a safety review will be triggered and study personnel will look at the records in an unblinded fashion to see if one mouthrinse is causing reactions. If that is the case, the mouthrinse study arm associated with adverse events will

be discontinued, but the mouthrinse arms associated with minimal adverse events will continue.

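### Serious adverse events are defined but no rule uses the definition: they share the 30-day reporting limit, the weekly review and the severity-blind 1-per-20 trigger with every other adverse event

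*Combined protocol and SAP*

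**What the plan says.** Section 7.3 defines adverse events and then, separately, an SAE, which "is generally defined as any untoward medical occurrence that results in death, is life threatening, requires inpatient hospitalization or prolongation of existing hospitalization", or leads to lasting disability or a congenital anomaly. Apart from the contents list, the term does not appear again.

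The rules that follow cover all adverse events together:

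- **Reporting (7.3 and 7.4).** "All adverse events will be reported to the IRB and the committee overseeing the study within 30 days".
- **Routine review (7.1 to 7.4 and 7.6).** "The investigator and team will meet weekly to review safety concerns, unanticipated problems or adverse events". There is no safety monitoring board. Section 9.4 adds that the internal quality control committee reviews adverse events.
- **Unblinded review by arm (9.4).** The condition is a raised count of events, "defined as more than 1 per every 20 patients), a safety review will be triggered". Study personnel then look at the records unblinded to see whether one rinse is responsible.
- **Follow-up (7.5).** Hospital referral and a call after one week, for any adverse event.

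Three other places bear on the point. Section 9.4 also says that medical problems in the facility go to the IRB when needed, without a time. Section 9.2 names staff who are "authorized to break the blinding if a patient suffers an allergic or adverse reaction to one of the mouthrinses", so that emergency workers can be told the product. Section 2.2 says: "A small fraction of patients (rare <1%) may be allergic to the mouth rinse". The adverse-effect tables in 2.2 and 7 list anaphylactic reactions with povidone-iodine.

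**The concern.** Defining an SAE normally serves to give it a faster report and a lower threshold for action. Here it does neither. Read literally, a life-threatening reaction and a passing local irritation have the same outer limit for reaching the IRB and the same weight in the rule that opens the data by arm.

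That rule is a rate above 5%. The hazard the protocol singles out, allergy, is put below 1%, so a serious reaction is likely to come as an isolated event. A frequency threshold is poorly suited to isolated events. At stake is whether a serious reaction to one rinse prompts a required look at that arm, or is left to the judgement of the weekly meeting.

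**Working it through.** **1. What applies to an SAE that does not apply to other adverse events?**

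| Rule | Any adverse event | SAE |
|---|---|---|
| Limit for reporting to IRB and overseeing committee (7.3, 7.4) | 30 days | same |
| Internal review (7.1 to 7.4, 7.6, 9.4) | weekly | same |
| Referral and one-week call (7.5) | yes | same |
| Weight in the 9.4 count | 1 | same |

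No row differs.

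**2. When does the 9.4 trigger fire?** The 30-day limit and the 1-per-20 rule are stipulated, so there is no derived figure to reproduce. The smallest count above 1 per 20 among n patients is floor(n/20) + 1:

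- n = 20: 2
- n = 80 (one full arm): 5
- n = 120 (one randomisation batch, 6 × 20): 7
- n = 480 (full enrolment, 6 × 80): 25

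A single event exceeds 1/20 only if the denominator is below 20, since 1/19 > 1/20 but 1/20 is not. From the 20th patient on, one SAE with no other events does not fire the trigger. With a pooled denominator, 6 SAEs in 120 or 24 in 480 would not fire it by themselves.

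**3. Illustration.** The documents give no SAE rate. The nearest figure is the ceiling of 1% in Section 2.2, for allergy of any severity. I take p = 0.01 in all six arms, count only these events, and use exact binomial tails. Section 9.4 does not say whether the count is pooled, per arm or per successive block, so each reading is shown:

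- Pooled at the end: P(X ≥ 25 | n = 480) = 5 × 10⁻¹¹.
- Pooled after one batch: P(X ≥ 7 | n = 120) = 0.02%.
- One given arm at the end: P(X ≥ 5 | n = 80) = 0.13%; any of six arms, 1 − (1 − 0.00129)⁶ = 0.8%.
- Any of 480/20 = 24 blocks: P(X ≥ 2 | n = 20) = 0.01686, and 1 − (1 − 0.01686)²⁴ = 33.5%.

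A running rate behaves differently early on, because any event among the first 19 patients fires it. At 1% that chance is 1 − 0.99¹⁹ = 17% if pooled. If kept per arm, it covers 6 × 19 = 114 patients, and the chance is 1 − 0.99¹¹⁴ = 68%. Under a running rate, then, whether one event is caught depends on when it occurs, not on how serious it is.

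**4. With a review on any SAE.** The chance of at least one review in 480 patients is 1 − (1 − p)⁴⁸⁰: 38.1%, 91.0% and 99.2% at assumed SAE rates of 0.1%, 0.5% and 1%. The expected number of SAEs is 480p: 0.48, 2.4 and 4.8.

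**The case against.** The strongest reply is that a serious reaction is far from ignored. Every adverse event reaches a weekly meeting of the investigators and coordinators. Emergency staff are called (5.3.1, 7), the blind can be broken for one patient (9.2), the participant can be removed (8), and the IRB can be told sooner than 30 days (9.4). Those who may break the blind include people who attend the weekly meeting. The products are commercial, and each participant rinses once.

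Most of this stands, and it rules out several stronger readings that a reader might infer.

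- *A serious reaction triggers no review at all.* The text contradicts this. What is missing is a faster report and a required unblinded look by arm.
- *The IRB will not know for a month.* Thirty days is an outer limit, not an expected delay. The documents give no enrolment rate, so the number randomised in the interval cannot be worked out.
- *The 30-day limit contradicts the weekly meeting.* That depends on which committee is meant. If it is the weekly team, it learns of the event at its next meeting; if it is the IRB, the only committee in Section 12, an internal weekly review and an external 30-day limit can coexist. The text does not settle it: 10.3.2 both describes an internal quality control committee and says there is none.
- *Several serious reactions are to be expected.* The 1% is a ceiling for allergy of any severity, stated before screening for self-reported allergy, and applied in step 3 to the saline arm as well. It is not an SAE rate.

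Nor would the count contain serious events alone; other adverse events add to it and could bring the trigger nearer. The reply still does not supply what is missing. The weekly review is by the study team and is not required to look by arm. The purpose stated for unblinding is to inform emergency care, and no rule carries that knowledge into a review of the arm.

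**Conclusion.** The point holds in a limited form. The SAE definition is not used by any rule. A serious event has the same 30-day outer limit as any other, in tension with the untimed IRB report in 9.4, and gets the same weekly review. From the 20th patient of the denominator on, a single SAE with no other events does not by itself trigger the unblinded arm-level review.

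These statements rest on the text and on counting, not on an assumed rate. The probabilities are illustrative: at 1% they run from effectively 0 (pooled, end of enrolment) through about 0.1% (one arm) to about 34% (blocks of 20), and a running rate would also catch an event among the first 19. An SAE rate below 1% would make the count less likely still to fire on such events alone.

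This is a gap in safety oversight that is cheap to close. It does not show that participants would go without care or without any review, and it does not affect the efficacy analysis.

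**What to change.** - **7.3 and 7.4.** Give SAEs their own reporting limit, shorter than that for other adverse events. The sponsor and IRB set its length. Reconcile it with the untimed IRB report in 9.4.
- **7.4, 10.3.2 and 12.** State which committee receives the reports, and resolve whether a quality control committee exists.
- **9.4.** Add that any SAE prompts the arm-level safety review regardless of the count. Keep the count rule for non-serious events, and say whether its denominator is pooled, per arm or per block. Say also whether the existing sentence on discontinuing an arm applies to a review prompted by an SAE. What follows for the arm stays with the reviewers and IRB.

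The new trigger should not be tied to breaking the blind. Section 9.2 allows that for any adverse reaction, so the trigger would again take no account of seriousness.

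The cost is a few sentences and an occasional review of an event that proves unrelated: at the assumed rates in step 4, about 0.5 to 5 reviews over the whole trial. No patients, visits or samples are added.
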